12.3.2 Analysis Sets

All subjects who receive at least one dose of the study drug will be included in the safety evaluation. All subjects who receive at least one dose of study drug and who have postbaseline efficacy data for the ORR will be included in the efficacy evaluations of the primary endpoint. All subjects who receive at least one dose of study drug and who have any postbaseline secondary efficacy data will be included in the efficacy evaluations of the secondary endpoints.

12.3.3 Demographic and Other Baseline Characteristics

Summary statistics will be presented for all treated subjects. Frequency tables for qualitative data will be provided. Medical and surgical history findings will be summarised using MedDRA terms.

12.3.4 Efficacy Evaluation

Tumour response will be assessed in imaging studies of CT or MRI scans after cycle 2 and subsequently every 8 weeks for the first 6 months and every 12 weeks thereafter.

The primary endpoint is ORR and will be calculated as defined in RECIST version1.1 and in Section 12.2.7. As part of secondary efficacy endpoints, DCR, TTP, Time to response (TTR), DOR, PFS and OS will also be determined as defined by RECIST version 1.1, metabolic response will also be determined as defined by PERCIST version 1.0.

In the particular context of the Simon Two-Stage approach, ORR will be analysed at the end of Stage 1 (and no later than after the 16-week visit of the last evaluable subject of the Stage 1 cohort for each PDAC and CRC cohorts). If the observed number of responders is below a predefined threshold, this part of the study will be stopped for futility. Otherwise, additional subjects will be treated to complete the planned enrolment. At the end of Stage 2, the null

hypothesis will be rejected depending on the total observed number of responders based on a predefined threshold.

At the end of the phase II, descriptive summaries will be provided for all primary and secondary efficacy endpoints. For the primary endpoint, final analysis will take into account the sequential sampling procedure of the design and the underlying binomial distribution assumed by the Simon Two-Stage design.

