Serum and whole blood ribonucleic acid samples will be stored for further biomarker analysis after the end of the study. Analysis of additional biomarkers from the biobank samples will be performed outside the scope of the main study and reported separately.

Statistical methodology

Statistical methodology in phase I

Safety

Continued monitoring of DLTs and toxicities will be performed during dose escalation. At the time of the SRC, an interim analysis of the DLTs, toxicities

and selected organ absorbed doses (kidney, liver and bone marrow) will be performed to guide the dose selection during the dose escalation part.

Biodistribution, radiation dosimetry, PK of ¹⁷⁷Lu-3BP-227

Descriptive summaries of PK and biodistribution parameters will be presented for each cohort over the treatment period.

Pharmacokinetics of 3BP-227

If 3BP-227 levels are measurable in plasma and urine, PK parameters of 3BP-227 will be derived using a noncompartmental approach. An attempt to build an integrated model taking into account PK, dosimetry, antitumour and safety data will be made.

Pharmacodynamics/Efficacy Analysis

In order to perform preliminary antitumour activity, ORR and DCR will be tabulated. Tumour response will be evaluated by the site investigator. Independent review of tumour assessment may be requested at the discretion of the sponsor. In both cases, response and progression will be evaluated using the revised RECIST guideline (version 1.1). Only subjects with measurable disease at baseline, who have received at least two administrations of ¹⁷⁷Lu-3BP-227 and reached the end of Cycle 2 or EOCT visit will be considered evaluable for response.

Statistical methodology in phase II

Efficacy Analysis

For phase II cohorts, tumour response will be assessed in imaging modalities of CT or MRI scans after Cycle 2 and subsequently every 8 weeks for the first 6 months and every 12 weeks thereafter. Images will be reviewed by an independent central review core laboratory. ORR, best overall response (BOR) and other efficacy parameters will be tabulated. Objective response rate will be calculated combining the number of subjects with a BOR of confirmed complete response (CR) or partial response (PR) per RECIST version 1.1.

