12.3 Statistical Methodology for Phase II

12.3.1 Sample Size Calculation

In case the antitumour activity is driven by a type of tumour, tumour-specific phase II cohort(s) will be initiated utilising an Optimal Simon Two-Stage design [33] to further evaluate the antitumour activity of ¹⁷⁷Lu-3BP-227. This approach tends to minimise the average number of subjects exposed to a new drug while addressing the scientific question.

The corresponding hypotheses (H) to be tested are: H_0 : ORR \leq ORR₀ versus H_1 : ORR \geq ORR₀ where ORR is the true objective response rate following 177 Lu-3BP-227 treatment and ORR₀ is the minimum objective response rate that would be considered to further clinical development.

For the purpose of the a priori sample size calculation, the following values are used for the PDAC cohort: ORR_0 is 17% and ORR is 35%. These values reflect the results from PDAC therapy [34] currently registered and are considered standard-of-care, and the level of expectation for the IMP prior to phase I.

Similarly, for the CRC cohort (blended population with regard to somatic mutations in BRAF and RAS genes), ORR₀ is 15% and ORR is 30% [35;36]. The value for ORR₀ reflects an estimated average result from different clinical studies that investigated CRC therapies in different populations [35, 36]; it is anticipated that based on lack of available and effective therapies an enrichment of poor-prognosis subjects with metastatic and recurrent CRC and prevalent mutations in BRAF and RAS will occur in the study population, while it is anticipated that it is unlikely for subjects with wild-type disease for which effective therapies exist over multiple lines of treatment to be enrolled. Subjects with somatic BRAF and RAS mutations are anticipated to have less exposure to prior treatment for metastatic disease compared with subjects with prevalent wild type BRAF or RAS tumours.

The assumptions forming the understanding of the expected efficacy of standard-of-care treatment and leading to sample size estimations may be updated based on results emerging from phase I and evolving scientific knowledge.

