In the first stage of the design, for the PDAC cohort, 16 subjects will be treated and evaluated for the ORR. If there are three or fewer responders in these 16 subjects, the cohort will be stopped for futility. Otherwise, 28 additional subjects will be treated and evaluated for a total of 44 subjects. The null hypothesis will be rejected if 12 or more responders are observed in the 44 subjects. This design yields a nominal one-sided type I error rate of 5% and a power of 80%, if the true response rate is 35%.

Similarly, in the first stage of the design, for the CRC cohort 19 subjects will be treated and evaluated for the ORR. If there are three or fewer responders in these 19 subjects, the cohort

will be stopped for futility. Otherwise, 36 additional subjects will be treated and evaluated for a total of 55 subjects. The null hypothesis will be rejected if 13 or more responders are observed in the 55 subjects. This design yields a nominal one-sided type I error rate of 5% and a power of 80%, if the true response rate is 30%.

Nonevaluable subjects will be replaced to meet the above numbers of evaluable subjects. A subject will be considered as nonevaluable and therefore replaced, if no evaluation post treatment is available or in case of drop-out before the 4-month visit for PDAC cohort and 8-month visit for CRC cohort with an insufficient follow-up duration (i.e. status being still "Stable Disease" as per RECIST version 1.1). In case of overenrollment, the first 16 evaluable subjects in the PDAC cohort and 19 subjects in the CRC cohort will be analysed at Stage 1 to make the decision about starting Stage 2. Assuming a non-evaluability rate of 20% for the PDAC cohort [34] and the CRC cohort [36], the number of subjects to be enrolled is expected to be approximately 55 and 70, respectively.

One, two or three further cohorts may be initiated (subject to results emerging from ongoing preclinical studies and antitumour efficacy seen during dose escalation and amending the current protocol) likely to enrol approximately 120 subjects with GC, SCCHN and/or ES.

In the case of acceptable tolerability and evident antitumour activity across all enrolled subjects in phase I, a phase II basket trial design will be utilised to study the antitumour activity of ¹⁷⁷Lu-3BP-227 in subjects with NTSR1 expressing tumours. The sample size will be described as part of a protocol amendment.

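### The 16-week limit on the phase II Stage 1 futility look can leave responses in late-enrolled subjects unconfirmed, and it does not fit the 8-month CRC evaluability rule

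*Protocol*

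**What the plan says.** All references are to the Protocol unless noted.

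- **Timing of the look.** Section 12.3.4, and the Synopsis in the same terms, require the Stage 1 analysis "no later than after the 16-week visit of the last evaluable subject of the Stage 1" cohort, for PDAC and CRC alike.
- **What counts as a response.** The Synopsis (phase II efficacy analysis) builds the objective response rate from subjects "with a BOR of confirmed complete response (CR) or partial response (PR"). The RECIST 1.1 text in Attachment 4 (its Section 4.6.1) requires confirmation in a non-randomised trial with response as primary endpoint. Its Section 4.4.3 puts the confirming assessment generally 4 weeks later.
- **Scan schedule.** Section 12.3.4 places scans "after cycle 2 and subsequently every 8 weeks for the first 6 months and every 12 weeks thereafter". Section 10.1.3 equates 8 weeks with the expected length of two cycles.
- **Stage 1 rule.** For PDAC, Section 12.3.1 says: "If there are three or fewer responders in these 16 subjects, the cohort will be stopped for futility". The CRC rule is three or fewer in 19.
- **Evaluability.** Section 12.3.1 replaces a subject in case of "drop-out before the 4-month visit for PDAC cohort and 8-month visit for CRC cohort" if the status is then still stable disease. Stage 1 uses the first 16 or 19 evaluable subjects.

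No section says how an unconfirmed response counts at the look. The SAP is limited to phase I dose escalation, so it neither settles this nor was meant to.

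**The concern.** Two timing rules do not fit together.

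First, a response seen at week 8 can be confirmed at week 16. A response first seen at week 16 cannot be confirmed before about week 20 with a dedicated scan, or week 24 on schedule. If the look is taken at the limit and counts only confirmed responses, such a response is missed.

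Second, a CRC subject in stable disease at week 16 may still drop out before month 8 and become nonevaluable. The set of 19, and the last evaluable subject who fixes the deadline, may therefore not be settled when the analysis is due. For PDAC the 4-month rule roughly matches 16 weeks, so there is no real conflict.

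With a boundary of three or fewer responders, one pending response can decide whether a cohort closes. A cohort closed in error cannot be recovered at the final analysis.

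**Working it through.** **Inputs (Section 12.3.1).**

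- PDAC: null rate p0 = 0.17, target p1 = 0.35, n1 = 16, stop at 3 or fewer, n = 44, reject at 12 or more.
- CRC: p0 = 0.15, p1 = 0.30, n1 = 19, stop at 3 or fewer, n = 55, reject at 13 or more.

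**Step 1: reproduce the plan.** With b(x; n, p) the binomial probability and r + 1 the rejection number:

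- False futility stop = Σ b(x; n1, p1) for x = 0 to 3.
- Power = Σ over x > 3 of b(x; n1, p1) × P(Bin(n − n1, p1) ≥ r + 1 − x).

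False stop, PDAC: 0.0010 + 0.0087 + 0.0353 + 0.0888 = 0.134 (rounded terms). False stop, CRC: 0.0011 + 0.0093 + 0.0358 + 0.0869 = 0.133.

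Power is 80.9% (PDAC) and 80.1% (CRC). Type I error is 0.046 and 0.048. The stated 80% and 5% are therefore right for the stated inputs, and a search returns these two designs as the Simon optimal ones. The reserve above 80% is 0.9 points for PDAC and 0.1 for CRC.

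**Step 2: what Step 1 assumes.** The same Stage 1 count enters the futility test and the final total, so every Stage 1 response must be known at the look.

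**Step 3: let some responses be pending.** Assume each response among the last k enrolled Stage 1 subjects is pending with probability s, independently, and is counted at the end if the cohort continues. Let X be the responses among the first n1 − k subjects, Y those among the last k, and C ~ Bin(Y, 1 − s) those already confirmed. The cohort continues if X + C > 3. It succeeds if X + Y plus the Stage 2 responses reaches r + 1. Power in %:

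| Subjects affected | PDAC, s = 10% | PDAC, s = 25% | CRC, s = 10% | CRC, s = 25% |
|---|---|---|---|---|
| last 2 | 80.3 | 79.3 | 79.6 | 78.8 |
| last 4 | 79.6 | 77.4 | 79.0 | 77.3 |
| last 8 | 78.1 | 72.9 | 77.9 | 74.0 |

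If instead a share of all Stage 1 responders is missed:

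| Share missed | PDAC power | CRC power |
|---|---|---|
| 5% | 78.1% | 77.4% |
| 10% | 74.7% | 74.3% |

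At 10% of all responders missed, the false stop is 20.7% (PDAC) and 20.4% (CRC).

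**Step 4: type I error.** Missing responses at the look only makes continuing harder. At 10% of all responders missed, type I error is 0.040 (PDAC) and 0.042 (CRC), below the design values.

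**Step 5: the CRC evaluability rule.** It removes drop-outs in stable disease, who are not responders. It changes which subjects form the 19, not the responder count directly, so the tables do not model it.

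**The case against.** The strongest reply is that the gap is narrow and the text provisional.

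- **Only late subjects are affected.** The limit is tied to the last evaluable subject. Those enrolled earlier have longer follow-up, and week-8 responses can be confirmed by week 16. This stands, and it is why the first table restricts the pending share to the last few subjects.
- **Confirmation at the look is not explicit.** Section 12.3.4 refers to Section 12.2.7, which does not mention confirmation, and the futility rule speaks only of responders. This stands in part: the rule is missing rather than wrong. The Synopsis and the appended RECIST text still point to confirmed responses.
- **Phase II will be amended.** Section 4.3 promises an amendment, and Section 12.3.1 leaves the number and length of cycles open. The week 8, 16 and 24 timeline therefore rests on 4-week cycles. This stands, but it makes the amendment the natural place for the repair. Longer cycles would move the first scan past week 8 and its confirmation past week 16.
- **An early look limits exposure to an inactive drug.** True, and the fix should keep the delay short.

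A reader might infer that the 80% power is lost, perhaps down to about 61%. The documents do not support that. Such a figure needs 25% of responses to be pending across every Stage 1 subject, and nothing in the protocol implies this. A reader might also infer that the 8-month rule makes CRC responders go uncounted. It does not: a stable subject still in follow-up is not a drop-out, and a stable drop-out is not a responder.

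**Conclusion.** The concern holds as a timing conflict and a missing rule, not as an error in the stated power. That power is correct on condition that all Stage 1 responses are known at the look, and the 16-week limit does not secure this for late-enrolled subjects.

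The size cannot be fixed from the documents, because they give neither an accrual rate nor a time-to-response distribution. Under the assumed 10-25% pending, the loss is about 2 points or less if two subjects are affected, and up to about 8 points (PDAC) or 6 points (CRC) if eight are. The error is conservative for type I error. The CRC evaluability conflict is real, but it bears on the composition of the 19 and is not quantified here.

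**What to change.** In the planned phase II amendment:

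1. State that if a cohort is at or below the futility boundary while unconfirmed responses are pending, the stop decision is held until their confirmatory scans. The delay is about 4 weeks with a dedicated scan, or about 8 at the next scheduled one.
2. Reconcile the 16-week limit with the 8-month CRC rule by stating which CRC subjects count as evaluable at Stage 1. Simply waiting for month 8 would postpone the look by roughly 19 weeks (8 × 30.4 / 7 ≈ 35, less 16).

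The hold recovers responses already seen but not yet confirmed. It does not recover those that first appear after the look.

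An alternative is to count unconfirmed responses for the decision to continue only. This costs no time. If some of them fail to confirm, however, the rule becomes more permissive and type I error can slightly exceed the design value. It cannot exceed that of the final test without a futility look, P(Bin(44, 0.17) ≥ 12) = 5.9% for PDAC and P(Bin(55, 0.15) ≥ 13) = 6.0% for CRC. Both are above the nominal 5%, so this option should be checked before it is adopted.

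The change is one of wording. Its downside is a short delay to the Stage 1 decision when responses are pending.

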12.3.5 Safety Evaluation

Safety analyses similar to phase I (see Section 12.2.5) will be performed for phase II, except for DLT assessments and 24-hour 3-lead ECG Holter measurements.

13 DATA HANDLING AND RECORD KEEPING

13.1 Data Collection

In compliance with Good Clinical Practice (GCP), the source data, i.e. medical records/medical notes, etc. should be clearly marked and permit easy identification of a subject's participation in the specified clinical study.

Source data identification and location, whether standalone documents or direct eCRF records, will be specified in a standalone document signed by the investigator(s).

The investigator must record all data relating to protocol procedures, study drug administration, laboratory data, safety, PK and pharmacodynamic data on the source documents and report requested data on eCRFs provided for the study (see Section 13.2).

To ensure accurate, complete and reliable data, the sponsor or its representative will provide instructional material to the study site(s), as appropriate. Training will be given during a start-up/initiation meeting for instructions on the completion/data entry of any source data documents and eCRFs.

The investigators or their designees must verify that all data entries in the eCRF are accurate and consistent with source data records. If certain information is not available for a particular timepoint and/or subject, specific instructions should be followed, e.g. to document that the procedure was either not done or not applicable.

For all subjects who received any administration of ¹⁷⁷Lu-3BP-227 the full obtained data set needs to be recorded in the eCRF.

For all screening failures who did not receive the screening IMP administration, a minimum of data including the primary reason for screening failure will be recorded in the eCRF.

13.2 Data Reporting

Electronic data capture (EDC) will be utilised for collecting subject data. The study site is required to have a computer and internet connection available for study site entry of clinical data. All entries in the eCRF will be made under the electronic signature of the person performing the action. This electronic signature consists of an individual and confidential username and password combination. It is declared to be the legally binding equivalent of the handwritten signature. Only sponsor authorised users will have access to the eCRF as appropriate to their study responsibilities. Users must have successfully undergone software application training prior to entering data into the eCRF.

13.3 Data Management

Details of all data management procedures, from the initial planning to the archiving of final data sets/documents following database freeze/lock will be documented in appropriate standalone data management and validation plan(s).

Data management will be conducted by a CRO approved by the sponsor. All data management procedures will be completed in accordance with the contracted CRO's standard operating procedures. Prior to data becoming available for processing at the assigned data management CRO, they will be monitored.

The sponsor will ensure that an appropriate eCRF is developed to capture the data accurately and that suitable queries are raised to resolve any missing or inconsistent data. The investigator will receive the data from the clinical study in an electronic format (PDF files), which will be an exact copy of the eCRF and will include the full audit trail, for archiving purposes and future reference.

Any queries generated during the data management process will also be tracked by the contracted data management CRO. It is the central study monitor's responsibility to ensure that all queries are resolved by the relevant parties.

The CRO will also ensure, via SAE reconciliation, that SAE data collected in the eCRF are consistent with SAE data held in the sponsor's GPS department (and vice versa).

The coding of AE, medical history and prior/concomitant medication/nondrug therapy terms will be performed by the sponsor's Central Group. Prior/Concomitant medications will be coded using the latest version of the WHO drug dictionary and AEs/medical history/nondrug therapy terms will be coded using the latest version of MedDRA.

13.4 Record Keeping

The investigator will keep records of all original source data. This might include laboratory tests, medical records and clinical notes.

During the prestudy and initiation visits, the monitor must ensure the archiving facilities are adequate and archiving/retention responsibilities of the investigator have been discussed.

Study documents should be retained until at least 2 years after the last approval of a marketing application in an ICH region and until there are no pending or planned marketing applications in an ICH region (that is at least 15 years) or at least 2 years have elapsed since the formal discontinuation of clinical development of the product. However, these documents should be retained for a longer period if required by applicable regulatory requirements or by an agreement with the sponsor. The investigator should take measures to prevent accidental or premature destruction of these documents. The final archiving arrangements will be confirmed by the monitor when closing out the study site. The sponsor will inform the investigator, in writing, as to when these documents no longer need to be retained.

If the principal investigator relocates or retires, or otherwise withdraws responsibility for maintenance and retention of study documents, the sponsor must be notified (preferably in writing) so that adequate provision can be made for their future maintenance and retention.

14 REGULATORY AND ETHICAL CONSIDERATIONS

14.1 Regulatory Considerations

The study will be conducted in compliance with IECs/IRBs, informed consent regulations, the Declaration of Helsinki and ICH Guidelines related to GCP. Any episode of noncompliance will be documented. The EDC system will comply with the FDA, 21 Code of Federal Regulations Part 11, Electronic Records, Electronic Signatures, and FDA, Guidance for Industry: Computerized Systems Used in Clinical Trials.

In addition, the study will adhere to all applicable international and local regulatory requirements.

All or some of the obligations of the sponsor will be assigned to a CRO.

An identification code assigned to each subject will be used in lieu of the subject's name to protect the subject's identity when reporting AEs and/or other trial-related data (see Section 4.6.1.1).

